1.7 Study Rationale

Patients with VT either refractory to catheter ablation or deemed medically too frail or challenging to treat with catheter ablation have limited options, with one-year survival below 20%. Preclinical data described above demonstrate that single fraction SBRT to discrete portions of the heart is feasible and may result in a reduction or elimination of VT. Overall safety and early efficacy of SBRT have not been rigorously studied in a prospective trial to date. The ENCORE therapy described herein provides for a potentially rapid and totally non-invasive method for delivering such therapy.

The purpose of this phase I/II study is to demonstrate the short-term safety and preliminary efficacy of ENCORE for patients with VT refractory to standard treatments.

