2.0 OBJECTIVES

2.1 Primary Objectives

1. Phase I - Demonstrate acute (≤ 90 days) safety of noninvasive stereotactic cardiac ablation radiotherapy (ENCORE). The **primary safety endpoint** is defined by a $\leq 20\%$ rate of serious adverse events (SAEs) using CTCAE v4.0 criteria that are possibly/probably/definitely related to study treatment, based on previously published data for expected invasive catheter-based VT-ablation procedures.
2. Phase II - Demonstrate preliminary efficacy of ENCORE. The **primary efficacy endpoint** is defined by the number of subjects with a reduction in ICD therapies (ATP and ICD shocks) comparing the period six months before ENCORE treatment to the six months after ENCORE treatment as adjudicated by continuous ICD monitoring. There will be a six-week “blanking period” after therapy to allow for ablation effect. For patients with PVC-induced cardiomyopathy, the primary efficacy will be any reduction in PVC burden based on ambulatory heart monitors.

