2.2 Secondary Objectives

1. Determine six-month and twelve-month survival (**overall mortality endpoint**) after treatment with ENCORE.
2. Determine **late toxicity endpoint** (>90 days to 12 months), as tracked prospectively after treatment using CTCAE v4.0 criteria.
3. Determine patient-reported health related **quality of life endpoint** (HRQOL) as measured by changes between pre-treatment and 6-week, 6-month, and 12-month post treatment scores on the standardized SF-36 questionnaire.

4. Evaluate **stricter efficacy endpoint** of ENCORE treatment, as defined by number of patients who have had 50% reduction in any VT therapies (ATP or ICD shocks) after ENCORE treatment (6 months before vs. 6 months after treatment, with a 6 week blanking period immediately after treatment). For patients with PVC-induced cardiomyopathy, the stricter efficacy will be >50% reduction in PVC burden based on ambulatory heart monitors.
5. Evaluate **strictest efficacy endpoint** of ENCORE treatment, as defined by number of patients who have had 95% reduction in any VT (ATP or ICD shocks) after ENCORE treatment (6 months before vs. 6 months after treatment, with a 6 week blanking period immediately after treatment). For patients with PVC-induced cardiomyopathy, the strictest efficacy will be abolition of PVC burden (<1%) based on ambulatory heart monitors.
6. Evaluate the **most clinically useful efficacy endpoint** of ENCORE treatment, namely, number of patients with reduction specifically in ICD shocks (6 months before vs. 6 months after treatment, with a 6 week blanking period immediately after treatment). For patients with PVC-induced cardiomyopathy, the most clinically useful efficacy will be improvement in cardiac function in the setting of any improvement in PVC burden.
7. Evaluate **longer-term durability endpoint** of ENCORE treatment, as defined by number of patients with reduction in VT therapies (ATP or ICD shock and ICD shock alone) during the early phase (treatment to 6 months, with 6 week blanking period) vs. the late phase (6 months to 1 year). For patients with PVC-induced cardiomyopathy, the longer-term durability efficacy will be persistence of any reduction in PVC burden based on ambulatory heart monitors during early phase vs. late phase.

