4.5 Evaluability Guidelines

Patients who complete the full intended dose of single fraction SBRT are evaluable for both the primary and secondary objectives.

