4.9 Duration of Follow up

Patients will be followed per protocol for 12 months following the completion of SBRT or until death, whichever occurs first. Follow-up is per the treatment calendar (see Section 8.0) and consists of routine clinical visits, 12-lead EKG and implanted device interrogations to evaluate toxicity and treatment response, and evaluation of QOL. Patients will be followed by office visits, phone calls, and review of medical record. Any additional follow-up and imaging will be obtained off-study as per routine clinical policies of the treating physician. After 12 months, patients will be followed at the discretion of the treating physicians. Patients will be tracked for clinical outcomes up to 5 years after completion of radiation via review of the medical record.

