9.0 MEASUREMENT OF EFFECT

1. Acute (≤ 90 days) safety of ENCORE will be defined as a $\leq 20\%$ rate of protocol-specific serious or serious adverse events (SAEs) using CTCAE v4.0 criteria that are possibly/probably/definitely related to study treatment, based on previously published data for expected invasive catheter-based VT-ablation procedures. Early stopping rules have been created such that if 5 or more patients develop ENCORE related SAEs out of the first 10 patients, this would be deemed significantly greater than 20% ($\alpha < 0.05$), and the trial will be halted.
2. Preliminary efficacy of ENCORE will be defined by the number of subjects with a reduction in ICD therapies (six month period before ENCORE treatment compared to six month period after ENCORE treatment) as adjudicated by continuous ICD monitoring.

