11.3 Analytic Plan for Primary Objectives

SAEs defined by CTCAE v4.0 criteria within 90 days of ENCORE that are possibly/probably/definitely related to study treatment will be recorded. ENCORE therapy will be deemed safe if the rate of SAEs is $\leq 20\%$. An additional early stopping rule dictates that if 5 or more out of the first 10 patients develop ENCORE related SAEs, the trial will be halted.

The number of ICD therapies delivered in the 6 month periods preceding and following ENCORE therapy will be recorded for each patient by interrogation of the ICD. ENCORE therapy will be deemed efficacious if there is a reduction in ICD therapies before and after treatment. The proportion of patients with efficacious ENCORE therapy will be calculated, with the intent of demonstrating at least 40% efficacy.

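### The plan does not say how to score an ICD patient who dies, is transplanted or stops being monitored before the 6-month window ends; applied literally, section 11.3 can count an early death as a success

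*Combined protocol and SAP*

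**What the plan says.** For ICD patients, section 11.3 sets out the data and the rule. The data: "The number of ICD therapies delivered in the 6 month periods preceding and following ENCORE therapy will be recorded for each patient". The rule: "ENCORE therapy will be deemed efficacious if there is a reduction in ICD therapies before and after treatment". The proportion of patients who meet the rule is then calculated, with a target of at least 40%.

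Sections 2.1 and 9.0 are less specific. In both, the number is a number of subjects: section 9.0 says "Preliminary efficacy of ENCORE will be defined by the number of subjects with a reduction in ICD therapies". Section 2.1 describes the comparison as "comparing the period six months before ENCORE treatment to the six months after ENCORE treatment as adjudicated by continuous ICD monitoring" and adds a six-week blanking period. Section 2.2 (items 4 to 6) uses "6 months before vs. 6 months after treatment, with a 6 week blanking period immediately after treatment". None of these sections divides by time observed or sets a minimum observed period.

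Two other sections decide who is counted and for how long. Section 4.5: "Patients who complete the full intended dose of single fraction SBRT are evaluable for both the primary and secondary objectives". Section 4.9: "Patients will be followed per protocol for 12 months following the completion of SBRT or until death, whichever occurs first".

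Death and transplant are foreseen. Section 6.0 provides for review of pathology in those patients, and section 2.2 makes six- and twelve-month survival a secondary endpoint. No section links either event to the efficacy endpoint. Patients with PVC-induced cardiomyopathy are scored on PVC burden and fall outside this point.

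**The concern.** A count that stops when the patient dies can only be lower for it. If the patient stays in the analysis and any fall is a success, a bad outcome raises the primary efficacy proportion. If instead a patient without a full window has no defined outcome, someone must choose one after the data are known. With 19 patients, one or two such choices can decide the result. Reporting survival separately shows the deaths but does not correct the proportion.

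**Working it through.** **1. The passages together.** Take an ICD patient with at least one baseline therapy who receives the full dose and dies in week 4. (The condition matters: inclusion criterion 4a also counts sustained VT, so a baseline count of ICD therapies is not guaranteed to exceed zero.)

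- Section 4.5: evaluable for the primary objective.
- Section 4.9: follow-up ends at death.
- Section 2.1: all observed time is blanked, so the counted total is 0.
- Section 11.3: 0 is below the baseline count, so there is a reduction and the patient is a success.

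A death after blanking usually gives the same result, but not always: a patient who dies in a VT storm after week 6 may have more therapies than at baseline.

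**2. The plan's own figures.** Inputs from section 11.2: n = 19, floor 40%, alternative 65%, alpha 0.0885, power 81.5%. No cut-off is stated. By exact binomial:

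- P(X ≥ 11 | 19, 0.40) = 0.0885
- P(X ≥ 11 | 19, 0.65) = 0.8145

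Both match, so 11/19 is the implied cut-off.

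**3. Early losses scored as success.** Let d patients be lost early and scored as successes, with the other patients at 40%. The chance of passing is P(Bin(19 − d, 0.40) ≥ 11 − d).

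| d | Needed from the rest | Chance of passing |
|---|---|---|
| 0 | 11 of 19 | 8.8% |
| 1 | 10 of 18 | 13.5% |
| 2 | 9 of 17 | 19.9% |
| 3 | 8 of 16 | 28.4% |

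**4. How likely such cases are.** The documents give no 6-month rate for enrolled patients, so the risk q is assumed. The chance of at least one case is 1 − (1 − q)^19. If all are scored as success, the per-patient success rate is q + (1 − q)(0.40).

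| q | At least one case in 19 | Success rate | P(X ≥ 11) |
|---|---|---|---|
| 5% | 62% | 0.43 | 14.0% |
| 10% | 86% | 0.46 | 20.9% |
| 20% | 99% | 0.52 | 39.0% |

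These are upper limits. They treat all 19 as ICD patients, while section 3.1 also admits PVC patients, and they score every loss as a success.

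**5. Comparison with survivors.** Assume an unchanged VT rate, single therapies following a Poisson model, a mean of 10 in the 26 baseline weeks, and at least one baseline therapy. The probability of a lower count after treatment is:

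- death at week 13 (7 counted weeks): 0.977
- survivor, blanking inside the 6 months (20 counted weeks): 0.666
- survivor, blanking before the 6 months (26 counted weeks): 0.455

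At 0.666, 11/19 is reached with probability 85% and no deaths, or 89% with one death scored as success. At 0.455 the figures are 20% and 27%. If blanking falls inside the window, the shorter counted period in survivors may therefore matter more than deaths do.

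**The case against.** **The window may be meant to be complete.** Section 2.1 speaks of continuous ICD monitoring and section 11.3 of 6-month periods on both sides. A patient dead at week 4 has no such period after treatment. This reading is at least as natural as scoring zero, so a reader who concludes that the plan definitely counts deaths as successes goes too far. What stands is that the plan does not choose. Section 4.5 also argues against simply dropping the patient, so on this reading an evaluable patient has no outcome.

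**Only section 11.3 specifies a count of therapies.** This stands. Sections 2.1 and 9.0 count subjects with a reduction. They do not exclude a rate, but they do not state one either.

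**The cut-off is inferred.** This stands. Section 11.3 states only at least 40%, which 8/19 (42.1%) meets. At 8/19 and a true rate of 40% the chance of passing is already 51%, and it rises to 63%, 74% or 83% with one, two or three early losses scored as success. Early losses push the result the same way under either cut-off.

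**Mortality.** A reader might take the one-year survival below 20% in section 1.7 to mean that most enrolled patients would die before the window ends. The documents do not support that. The figure describes the background population, and exclusion criteria 2 and 6 remove NYHA Class IV patients and those judged unlikely to live 12 months in the absence of VT.

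**Scoring transplant or lost monitoring as failure is debatable.** This stands in part. Section 5.1 treats progression of heart failure as natural history and leaves transplant decisions unaffected by enrolment. The case for non-success is clearest for death. For the others the main need is that the choice be made in advance.

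**Conclusion.** The concern holds as a gap in the primary efficacy endpoint that should be fixed. For ICD patients the outcome after death, transplant or lost monitoring within the window is unspecified, and the literal rule can credit an early death as benefit.

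The size is a false-positive rate of 13.5%, 19.9% or 28.4% instead of 8.8% for one, two or three such patients. This rests on the implied 11/19 cut-off, on the other patients succeeding at the plan's own 40% floor (not at a no-effect rate), and on an assumed number of cases. Any PVC enrolment lowers the number of patients at risk.

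It does not follow that early death is the main source of false success; the shorter counted period in survivors is a separate and possibly larger one. Nor is this more than a correction of endpoint wording in a 19-patient single-arm study of preliminary efficacy that also reports six-month survival.

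**What to change.** In sections 2.1, 9.0 and 11.3, and in section 2.2 items 4 to 7 (each over its own window):

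- Keep every treated ICD patient in the denominator.
- Score death before the window ends as non-success.
- Pre-specify transplant and loss of monitoring (device removed, or no further interrogation) as non-success in the primary analysis.
- Report the number of patients for each reason.
- Add a sensitivity analysis that compares therapies per month alive and monitored after blanking with the baseline monthly rate. It shows how far the result depends on the scoring of transplant and lost monitoring, and it handles the shorter counted period in survivors. Patients with no time after blanking stay non-success.

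This takes a few sentences. Deaths and device interrogations are already collected, and section 6.0 already provides for review of transplanted patients.

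The price is a lower efficacy proportion and lower power. With d such patients scored as non-success and the others at 65%, power is P(Bin(19 − d, 0.65) ≥ 11): 72.8%, 61.9% or 49.0% for d = 1, 2 or 3, against 81.5% with none. With the others at 40%, the false-positive rate falls to 5.8%, 3.5% or 1.9%.

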3.0 PATIENT SELECTION

3.1 Inclusion Criteria

1. DOCUMENTED VT:
 - a. Patient must have documented sustained monomorphic ventricular tachycardia as documented on either a 12-lead ECG or intracardiac ICD interrogation
 - OR—
 - b. Monomorphic PVCs documented on a 12-lead ECG.
2. ANTIARRHYTHMIC MEDICATION: Patient must have failed or become intolerant to at least one antiarrhythmic medication (amiodarone, sotalol, or mexiletine).
—AND—
3. CATHETER ABLATION: Patient must have failed at least one invasive catheter ablation procedure, or have a contraindication to a catheter ablation procedure (e.g., LV thrombus, severe pulmonary disease), or have VT thought to arise from a protected location (e.g., epicardial VT with history of previous cardiac surgery).
4. MINIMUM VT BURDEN: Patient must have either:
 - a. At least 3 VT episodes (sustained VT, ICD ATP or ICD shock) over previous 6 months prior to enrollment
 - OR—
 - b. >20% PVC burden with a cardiomyopathy (LVEF<50%)
5. Patient must be deemed medically fit for stereotactic body radiation therapy by the treating physician.
6. Patient must be \geq 18 years old.
7. Patient must be able to understand and be willing to sign an IRB approved written informed consent document.

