4.10 Management of ICD Programming and Antiarrhythmic Medications During Follow up

ICD programming parameters and antiarrhythmic medication dosing should be patient-specific decisions, left to the treating physician taking into account risks and benefits of the various strategies. Ideal settings are suggested below:

- ICD programming should include a zone for detection at least 20ms slower than the slowest clinical or induced VT. ICD therapy may or may not be programmed to deliver therapy in this zone, subject to decisions about patient symptoms and tolerances during VT.
- Antiarrhythmic medications should be maintained at pre-treatment doses for at least the first 6 weeks, barring any development of adverse medication effect.
- With each subsequent visit after the first 6 weeks, doses of at least one antiarrhythmic medication should be reduced if no VT has been observed on ICD device check.

- If not contraindicated, oral anticoagulation is preferred during the first month after treatment (warfarin, dabigatran, rivaroxaban, apixaban or edoxaban) to minimize risks of stroke.

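### The efficacy rules have no provision for a repeat ablation, other VT procedure or transplant inside the 6-month window, so a fall in ICD therapies that follows one is scored as ENCORE success

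*Combined protocol and SAP*

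**What the plan says.** Section 2.1 defines the primary efficacy endpoint as "the number of subjects with a reduction in ICD therapies (ATP and ICD shocks) comparing the period six months before ENCORE treatment" with the six months after it, with a six-week blanking period. Section 9.0 repeats it: "Preliminary efficacy of ENCORE will be defined by the number of subjects with a reduction in ICD therapies". Section 11.3 gives the scoring rule, "ENCORE therapy will be deemed efficacious if there is a reduction in ICD therapies before and after treatment", and aims to show at least 40% efficacy. The stricter endpoint in 2.2 counts responders "as defined by number of patients who have had 50% reduction in any VT therapies (ATP or ICD shocks) after ENCORE treatment". It, the 95% endpoint and the shock-only endpoint share the same windows: "6 months before vs. 6 months after treatment, with a 6 week blanking period immediately after treatment". Patients with PVC-induced cardiomyopathy are scored on PVC burden instead and, for one secondary endpoint, on cardiac function as well.

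On who is analysed, 4.5 says: "Patients who complete the full intended dose of single fraction SBRT are evaluable for both the primary and secondary objectives". On care during follow-up, 4.10 says: "ICD programming parameters and antiarrhythmic medication dosing should be patient-specific decisions, left to the treating physician". That section covers device programming, antiarrhythmic drugs and anticoagulation, but not procedures. Section 5.1 adds that enrolment does not affect transplant decisions.

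The sections on objectives, treatment, follow-up, measurement of effect and statistics contain no rule that bars, censors or separately scores a VT procedure or transplant in the window.

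**The concern.** There is no control arm, so the before/after change in each patient is the only evidence that ENCORE works. Continuous ICD monitoring establishes how many therapies were delivered, but not why the number fell. If VT persists after ENCORE and the patient then has another ablation, the quiet weeks that follow are credited to ENCORE.

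Such rescue is possible. One entry route in 3.1 is "Patient must have failed at least one invasive catheter ablation procedure, or have a contraindication to a catheter ablation procedure", and a failed ablation does not rule out another. Rescue would go mainly to patients with continuing VT, whose ENCORE result ought to read as failure. With 19 patients, a few such conversions would matter. Without a written rule, the analyst has to decide how to treat them after seeing who was rescued.

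**Working it through.** **1. The plan's own figure.** Section 11.2 gives n = 19, 40% against 65%, α = 0.0885 and power 81.5%, but no cutoff. With an exact binomial, P(X ≥ 11) is 0.0885 at 40% and 0.8145 at 65%. Both figures match, so the cutoff is inferred to be 11 of 19.

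**2. One converted patient.** This adds 1/19 = 5.3 percentage points. If exactly one true failure is converted, 11/19 is reached with 10 true responders, so the chance of passing becomes P(X ≥ 10):

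| True rate | P(X ≥ 11) | P(X ≥ 10) |
|---|---|---|
| 30% | 0.011 | 0.033 |
| 35% | 0.035 | 0.088 |
| 40% | 0.0885 | 0.186 |

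**3. Which endpoints can flip, on expected counts.** Assumptions: 26 therapies in the 26 weeks before ENCORE (one per week); raw counts for weeks 6–26 after it, since the plan mentions no rescaling; R = rate after ENCORE / rate before; rescue at week 12 cuts the rate by a fraction c. The documents give neither the timing nor c.

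- Without rescue: 20R.
- With rescue at week 12: R[6 + 14(1 − c)], which is 16.5R, 14.4R, 13R or 9.5R for c = 25%, 40%, 50% or 75%.
- Primary (fewer than 26): a patient passes without rescue if R < 26/20 = 1.30. Rescue changes the score only from R = 1.30 up to 26/13 = 2.0 (c = 50%) or 26/9.5 = 2.74 (c = 75%). An unchanged-rate patient already passes, 20 against 26. The shock-only rule has the same form.
- 50% endpoint (at most 13): rescue changes the score for R above 13/20 = 0.65, up to 13/13 = 1.0 (c = 50%) or 13/9.5 = 1.37 (c = 75%). An unchanged-rate patient crosses only if 6 + 14(1 − c) ≤ 13, that is c ≥ 50%. At c = 40% the count is 14.4 and the patient still fails.
- 95% endpoint (at most 1.3): rescue changes the score only for R between 1.3/20 = 0.065 and 1.3/9.5 = 0.137 (c = 75%), which is a narrow band.

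**4. With chance variation.** Assumptions: Poisson counts after ENCORE, baseline count held fixed, R = 1, rescue at week 12. The mean is the baseline × [6 + 14(1 − c)]/26. A baseline of 3 is taken from the minimum VT-episode count in 3.1; those episodes include sustained VT as well as ICD therapies.

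| | No rescue | c = 25% | c = 40% | c = 50% | c = 75% |
|---|---|---|---|---|---|
| 50% reduction, baseline 26 (count ≤ 13) | 7% | 24% | 42% | 57% | 90% |
| 50% reduction, baseline 3 (count ≤ 1) | 33% | 43% | 51% | 56% | 70% |
| Any reduction, baseline 3 (count ≤ 2) | 59% | 70% | 77% | 81% | 90% |

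At a baseline of 26, the chance of any reduction is already 89% without rescue.

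**5. Cost of scoring rescue as failure.** If an assumed 5% of true responders are reclassified, 0.65 × 0.95 = 0.6175 and P(X ≥ 11) = 0.723. At 10%, 0.65 × 0.90 = 0.585 and P(X ≥ 11) = 0.617.

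**The case against.** The strongest reply is that the gap will seldom matter. Sections 1.4 and 1.7 describe patients with few options left, refractory to ablation or poor candidates for it. Those who enter with a contraindication or a protected VT location will rarely have catheter rescue. No rescue rate is given, so a single conversion is a hypothetical. This stands, and it is why no overall size is claimed.

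The effect of rescue is also assumed. Section 1.2 reports recurrence after ablation, not a reduction in rate, and many candidates have already failed one. Showing cuts from 25% to 75% answers this in part: the direction holds throughout, but the size varies greatly.

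A reader might infer that every efficacy endpoint is inflated alike, or that the 40% conclusion is unsound. The documents do not support that. On expected counts the primary and shock-only scores move only for patients who worsened by 30% or more, and the 95% score hardly moves. The 50% endpoint, which is the most exposed, is only described in 11.4, with no test or threshold.

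Nor can a net upward bias be inferred. Section 4.10 suggests holding drugs steady for six weeks and then reducing at least one at each later visit if no VT is seen. That works against ENCORE in patients who respond.

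Finally, counting rescue as failure can penalise a true responder treated for residual VT, or a patient rescued during the blanked weeks before an effect was expected. This stands too, and is the reason to keep the count-only result in view.

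**Conclusion.** The omission is real and worth closing. As written, the rules credit ENCORE with any fall that follows another VT procedure or a transplant in the window, including a fall in PVC burden in the PVC group. This is more than missing detail, because the stated rule can give a wrong score for a patient.

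The effect is most serious on the 50% secondary endpoint, where rescue can carry a patient with no ENCORE effect across the line. The primary is exposed through patients who worsened and, by chance, through patients with few baseline therapies. How much the trial result would shift is unknown. It depends on a rescue rate, a rescue time and a rescue effect that the documents do not give, and the 11/19 cutoff is itself inferred from 11.2. It is a low-cost improvement, not a flaw that overturns the design, and confidence in it is medium.

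**What to change.** In 2.1, 2.2 and 11.3, score as a non-responder any patient who, between ENCORE and the end of the 6-month window, has a catheter ablation for VT or PVCs, repeat cardiac SBRT, another VT procedure, or a heart transplant for any reason. Including every transplant avoids a judgement on its cause. Report the count-only result and a list of in-window procedures beside it.

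Add one sensitivity analysis that also scores a new or escalated antiarrhythmic drug given for VT after ENCORE as non-response. State with it that 4.10 suggests drug reduction in patients without VT.

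The cost is wording and one extra analysis, with no more patients or visits and no change to care. The downside is that true responders who are rescued or transplanted become failures, each lowering the response rate by 5.3 percentage points. If an assumed 5% or 10% of responders are reclassified, power at 11/19 falls from 81.5% to 72% or 62%. The count-only result keeps those patients visible.

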11.2 Sample Size Justification

A total of 19 patients will be enrolled, which provides an optimal balance between assuring a high likelihood of safety (Phase I) with a preliminary assessment of efficacy (Phase II).

For the phase I component, the baseline rate of SAEs for catheter ablation is assumed to be 10-15%. Given the population being studied and a reasonable expectation that patients may be at a higher than typical risk of toxicity from any salvage therapy, we assume that SAE rates up to 20% would be clinically acceptable. Having said that, given that this is a totally noninvasive technique, it may well be that rates of toxicity are lower than that expected with catheter ablation. After exploring patient ranges from 15-25 patients, it was determined that 19 patients would provide a 75.4% power to detect an SAE rate about 20% (range, 5%-20%, $\alpha = 0.0829$).

For the phase II component, while some single institution series report much higher success rates, the baseline efficacy rate of catheter ablation in prospective trials ranges from 50-65%. As this is a salvage therapy in a high risk population, we assume that efficacy rates as low as 40% would be clinically acceptable. Using the 19 patient sample determined above, it was determined that 19 patients would provide 81.5% power to determine that ENCORE is not worse than 40% effective for the treatment of VT (range, 40-65%, $\alpha = 0.0885$).

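### Section 11.3 gives no responder cut-off for the primary efficacy endpoint, so 8 to 10 responders of 19 could be called either success or failure

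*Combined protocol and SAP*

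**What the plan says.** Section 11.2 fixes the sample size ("A total of 19 patients will be enrolled") and sets the efficacy reference: "we assume that efficacy rates as low as 40% would be clinically acceptable". It then states that "19 patients would provide 81.5% power to determine that ENCORE is not worse than 40% effective for the treatment of VT", with a range of 40-65% and alpha = 0.0885. The upper end of that range agrees with the benchmark given in the same paragraph: "the baseline efficacy rate of catheter ablation in prospective trials ranges from 50-65"%. Section 11.2 gives no number of responders and does not say whether the test is one- or two-sided.

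Section 11.3, the analytic plan for the primary objectives, counts a patient as a success if ICD therapies fall after treatment. It then says: "The proportion of patients with efficacious ENCORE therapy will be calculated, with the intent of demonstrating at least 40% efficacy". That is the only efficacy threshold in the section.

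Sections 2.1 and 9.0 define the endpoint without a cut-off; in 9.0, "Preliminary efficacy of ENCORE will be defined by the number of subjects with a reduction in ICD therapies". Section 11.4 adds none.

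**The concern.** The 40% in 11.3 can be read in two ways. It may be the null value of the test powered in 11.2, so that success means rejecting a true rate of 40%. Or it may be a benchmark for the observed proportion, so that success means seeing 40% or more. The two readings need different numbers of responders, and the text does not say which applies.

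This is a single-arm trial, so the efficacy conclusion rests on this threshold alone. If the count falls where the readings disagree, the verdict can be chosen after the data are seen. If the literal reading is used, the alpha and power in 11.2 do not describe the criterion applied.

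**Working it through.** **Inputs.** n = 19, reference rate p0 = 0.40, alternative p1 = 0.65 (upper end of the stated range), stated alpha 0.0885 and stated power 81.5%, all from section 11.2. The 40% threshold is from section 11.3. All 19 patients are taken as evaluable.

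**Step 1: reproduce the figures in 11.2.** For a rule of at least r responders, alpha = P(X ≥ r | n = 19, p = 0.40) and power = P(X ≥ r | n = 19, p = 0.65), with X binomial.

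| Rule | Observed proportion at the cut-off | P(pass) at 40% | P(pass) at 65% |
|---|---|---|---|
| ≥ 8 | 42.1% | 0.5122 | 0.9886 |
| ≥ 9 | 47.4% | 0.3325 | 0.9653 |
| ≥ 10 | 52.6% | 0.1861 | 0.9125 |
| **≥ 11** | **57.9%** | **0.0885** | **0.8145** |
| ≥ 12 | 63.2% | 0.0352 | 0.6656 |

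Only r = 11 matches both stated figures. The reversed test (null 65%, reject at 9 or fewer) gives 0.0875 and 0.8139, so it does not match. The figures in 11.2 are right, and they are one-sided.

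**Step 2: the cut-off under the literal reading.** 7/19 = 36.8%, below 40%. 8/19 = 42.1%, above 40%. The literal cut-off is therefore 8.

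**Step 3: where the readings disagree.** 7 or fewer fails both and 11 or more passes both, so the disputed results are exactly 8, 9 and 10. Each entry in the 40% column above is also the one-sided exact p-value for a result at that count: 0.512, 0.333 and 0.186 for 8, 9 and 10, all above 0.0885. The exact (Clopper-Pearson) one-sided lower bounds at the matching level of 1 − 0.0885 = 91.15% are:

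- 8/19: 25.7%
- 9/19: 30.3%
- 10/19: 35.1%
- 11/19: 40.0%

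**Step 4: chance of a disputed result.** P(8 ≤ X ≤ 10) = P(X ≥ 8) − P(X ≥ 11).

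- True rate 40%: 0.5122 − 0.0885 = 0.424 (rounded from unrounded terms)
- True rate 50%: 0.497
- True rate 65%: 0.9886 − 0.8145 = 0.174

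**Step 5: what each reading lets through.**

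| True rate | Literal, ≥ 8/19 | Rule behind 11.2, ≥ 11/19 |
|---|---|---|
| 30% | 18.2% | 1.1% |
| 35% | 33.4% | 3.5% |
| 40% | 51.2% | 8.85% |
| 65% | 98.9% | 81.5% |

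**Step 6: can 11.3 be assumed to carry over the rule behind 11.2?** The safety criterion in the same section suggests not. It says "ENCORE therapy will be deemed safe if the rate of SAEs is" at or below 20%, a comparison of the observed rate, which 3/19 (15.8%) meets. The safety figures in 11.2 (alpha 0.0829, power 75.4%) belong to a rule of at most 1 event: P(X ≤ 1 | 0.20) = 0.0829 and P(X ≤ 1 | 0.05) = 0.7547, which gives 75.4% if truncated. At most 3 events would give P(X ≤ 3 | 0.20) = 0.455. So for the other primary endpoint, 11.3 as written is not the test behind 11.2.

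**The case against.** The best case for the plan is that 11.2 and 11.3 belong together. Section 11.2 fixes n, the 40% reference, the range, alpha and power, and these identify one exact rule that anyone can recover before the data arrive. The verb in 11.3, demonstrating, is inferential and echoes the aim in 11.2, whereas the safety sentence is openly an observed-rate rule; that contrast could mean that efficacy is meant as a test. A team claiming success at 8/19 would have to disregard its own stated alpha. The trial is also small, calls its efficacy assessment preliminary, and has only a 17.4% chance of a disputed result at its design alternative.

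Parts of this stand. The test reading is plausible and may be the intended one, and nothing in 11.2 is miscalculated. Because the plan calls 40% acceptable, passing at a true 40% is not plainly a wrong decision on the literal reading; the pass rates of 33.4% at 35% and 18.2% at 30% are the clearer errors there.

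It does not settle the point. A primary success rule should not have to be worked back from an alpha. Section 11.1 shows that the plan prints the test and the count when it wants a rule (5 or more of the first 10), and the efficacy paragraph prints neither. Calling 40% clinically acceptable also makes the literal benchmark a natural reading. A preliminary aim does not excuse a stated alpha and power that may not belong to the criterion used.

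**Conclusion.** The concern holds and should be fixed before analysis. The alpha and power in 11.2 describe a rule of at least 11 of 19, while the only efficacy threshold in 11.3 is met literally at 8 of 19. For 8, 9 or 10 responders the plan gives no settled verdict, and the probability of that runs from 17.4% at a true 65% to 49.7% at 50%.

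This rests on two assumptions. The count of 11 is inferred from its match to both stated figures, not quoted from the plan. All 19 patients are taken as evaluable for efficacy; with fewer, the cut-off and error rates change.

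**What to change.** Add one sentence to 11.3, for example: efficacy is demonstrated if at least 11 of 19 evaluable patients respond (one-sided exact binomial test against 40%, alpha 0.0885, power 81.5% at a true rate of 65%); the exact one-sided 91.15% lower confidence bound will be reported. Name the level of the bound, because the one-sided 95% bound at 11/19 is 36.8% and would seem to contradict a success.

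Section 4.5 ties evaluability to treatment: "Patients who complete the full intended dose of single fraction SBRT are evaluable for both the primary and secondary objectives". If fewer than 19 patients qualify, restate the rule:

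- n = 18, at least 11: alpha 0.058, power 72.8%
- n = 17, at least 10: alpha 0.092, power 78.7%
- n = 17, at least 11, if alpha may not exceed 0.0885: alpha 0.035, power 61.9%

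If an observed proportion of 40% or more is what was meant, say so. Then either give its actual pass probabilities in 11.2 (0.512 at a true 40%, 98.9% at 65%) or, more sensibly, call the comparison descriptive and delete the alpha and power.

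The cost is one sentence and no patients. The downside is a stricter bar than the literal text (11 responders instead of 8) or, on the other route, the loss of the stated alpha and power.
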